Clinical Investigation Plan

CP362

Investigation of a new rectal catheter for users of transanal irrigation

April 2024 – June 2024

Master

Version 4.0

CHANGE LOG

VERSION ISSUED BY NUMBER (INITIALS) COMMENTS (MAJOR CHANGES SINCE		COMMENTS (MAJOR CHANGES SINCE LAST REVISION)
1.0		First approved version
2.0		Study design-picture changed, LPO changed to June 2024, section 5.3.2 has been updated, section 5.3.6 has been added, additional comment field added to Visit 1 and Visit 2 and unscheduled visit added
3.0		
4.0		Changes made to section. 4.1, 6.2.1, 8.1, 8.2, and 14.4

This confidential document is the property of Coloplast A/S. No unpublished information contained herein may be disclosed without written approval of Coloplast A/S.

1

SYNOPSIS OF THE CLINICAL INVESTIGATION

Title:

Investigation of a new rectal catheter for users of transanal irrigation.

Investigational device and comparator device:

The investigational device in this clinical investigation is a newly developed rectal catheter (CP362 rectal test catheter) used for transanal irrigation (TAI).

The investigational device is a rectal catheter, that will be tested and will be used together with the CE-marked Peristeen Plus TAI system

CP362 rectal test catheter and Peristeen Gel comprises the investigational device.

In this clinical investigation the CE-marked Peristeen Plus rectal balloon catheter will be used as a comparator device. The Peristeen Plus rectal balloon catheter will also be used together with the Peristeen Plus TAI system.

The investigational device is not a CE-marked device, and it will be provided by Coloplast A/S. Both the comparator device and the Peristeen Gel will also be provided by Coloplast A/S.

Intended use:

Both the investigational device and the comparator device are accessories to the Peristeen Plus TAI system. The Peristeen Plus TAI system is intended to perform TAI, which is an effective bowel management technique that empties faeces from the lower colon in a controlled manner, allowing patients to be in control of when and where they empty their bowels. The Peristeen Gel is intended to be used with the CE-marked Peristeen Anal Plug to make insertion easier.

Objectives:

Primary objective:

The primary objective is to obtain indications that a new rectal catheter can be used for TAI.

Secondary objective:

The secondary objective will include assessment of safety

Design of the investigation:

The clinical investigation is an exploratory, randomised controlled, open-labelled, crossover investigation. The clinical investigation will be conducted as a multi-centre clinical investigation in two different clinical investigation sites

The aim is to randomize 20 subjects who are currently using a rectal balloon catheter for TAI procedure. Furthermore, the subjects must have been using a rectal balloon catheter for at least four weeks prior study inclusion.

The total clinical investigation duration for each subject will be up to 17 days, consisting of three site visits: Screening Visit (V0), Baseline Visit (V1) and Visit 2 (V2).

V0 and

V1 can be performed on the same day. V1 and V2 must be scheduled on a day where the subject normally performs the TAI procedure, and V2 must furthermore be scheduled within 14 days after V1. At V1 and V2 the TAI procedure will be performed in a hospital setting.

Expected duration of the clinical investigation:

The clinical investigation will be conducted from:

First patient in (FPI): April 2024

Last patient out (LPO): June 2024

Database lock (DBL): June 2024

Clinical Investigation Report (CIR): November 2024

Primary endpoint:

The primary endpoint is: Was it possible to perform transanal irrigation (assessed after irrigation at V1 and V2)? (Yes/no).

Population/subjects:

As this is an exploratory clinical investigation it is assumed that 20 randomized subjects will be adequate for obtaining indications on performance and feasibility of the investigational device.

The subjects included in the clinical investigation must comply with the inclusion- and exclusion criteria listed below:

Inclusion criteria	Exclusion criteria
Has given written informed consent	Has known anal or colorectal stenosis
ts at least 18 years old	Has active/recurrent colorectal cancer
Has full legal capacity	is within 3 months of anal or colorectal surgery
Has used trans anal irrigation with balloon	Is within 4 weeks of endoscopic polypectomy
catheter for at least four weeks prior to inclusion	Has ischaemic colitis
Performs trans anal irrigation minimum 3 times/week	Has acute inflammatory bowel disease
	Has acute diverticulitis
is able to follow study procedures assessed by investigator	Is participating in any other clinical study that may interfere with this study assessed by investigator
	is pregnant or breastfeeding

LIST OF ABBREBIATIONS

ABBREVIATION	WRITTEN OUT	EXPLANATION (IF APPLICABLE)
ADE	Adverse Device Effect	See section 16.2

1.2. Investigators

Details of sites and Principal Investigators (PI) are listed in the list below.

COORDINATING PRINCIPAL INVESTIGATOR	PRINCIPAL INVESTIGATOR		

2. Justification for conducting the clinical investigation

This is an exploratory clinical investigation (first in human) investigating the feasibility and performance of a new rectal catheter for TAI procedure.

Based on recent consensus, TAI should be considered as a therapeutic modality for patients with bowel dysfunction failing to respond to conservative bowel management (e.g., laxative and diet), before resorting to invasive interventions (such as antegrade enemas, sacral nerve stimulation and stomas)¹⁻⁷. This was also one of the conclusions in a meta-analysis comparing treatments for faecal incontinence⁸. The main components of the Coloplast A/S produced Peristeen Plus TAI system consist of a control unit (featuring a pneumatic bulb pump and a four-position rotary switch), a water bag (featuring a pressure relief valve) and a pre-coated rectal balloon catheter or cone catheter.

The data will not be used for conformity assessment; therefore, the study will be submitted to the Danish Ethical Committee (EC) under Article 82 of the Medical Device Regulation EU 2017/245.

3. Objectives

The aim of this clinical investigation is to explore the feasibility of performing TAI by using the newly developed investigational device, CP362 rectal test catheter, compared to the CE-marked Peristeen Plus rectal balloon catheter.

3.1. Objectives

Primary objective:

The primary objective is to obtain indications that a new rectal catheter can be used for TAI.

Secondary objective:

The secondary objective will include assessment of safety

4.1. Description of investigational device

The investigational device will be classified according to MDR EU 2017/745 and MDCG-2021-24 Guidance on classification of medical devices.

CP362 test catheter will be classified as Class I, based on rule 5:

"All invasive devices with respect to body orifices, other than surgically invasive devices, which are not intended for

connection to an active medical device or which are intended for connection to a class I active device are classified

as:

- Class I if they are intended for transient use"

The test catheter is invasive and intended for transient use, therefore, the device is class I.

CE-marked Peristeen Plus TAI system is Class I, non-sterile, and CE-marked Peristeen Gel is Class IIb, nonsterile.

TAI procedure is performed by introducing water into the rectum using a rectal catheter. The water fills up in the large intestine and causes peristaltic movement in the bowels. After introducing the appropriate amount of water into the bowel, water and stools are emptied into the toilet, and the rectal catheter is discarded.

4.1.1. Manufacturing

Responsible for manufacturing the investigational device:

Coloplast A/S

4.2. Identification and traceability of the devices

All investigational devices are labelled as per regulations and included "exclusively for clinical investigation" on the label. The devices are also identified with a study number, device name/code, and item/lot number and is accounted for through a sponsor accountability log.

Upon EC approval, investigational devices and comparator devices will be shipped to the principal investigator or designee at sites. Additionally, all investigational devices and comparator devices will be accounted for and documented on a site accountability log. The receipt and disposition of all investigational devices and comparator devices will be verified through monitoring. All unused devices will be returned to Coloplast A/S at the conclusion of the study.

4.3. Intended use of the device in the clinical investigation

The investigational device is intended to perform TAI procedures together with the CE-marked Peristeen Plus TAI system. TAI is an effective bowel management technique that empties faeces from the lower colon in a controlled manner, allowing patients to be in control of when and where they empty their bowels.

Contraindications for use are identical to the contraindications for the Peristeen Plus rectal balloon catheter. The contraindications are: Known anal or colorectal stenosis, active or recurrent colorectal cancer, anal or colorectal surgery within three month, endoscopic polypectomy within four weeks, ischaemic colitis, acute inflammatory bowel disease or acute diverticulitis.

Clinical Investigation Plan_

4.4. Intended population for the device

The intended population for the new CP362 rectal test catheter is adults who are currently using a rectal balloon catheter for TAI procedure.

4.5. Handling of the investigational device

The handling of the investigational device is described in detail in the Instruction for Use (IFU) (see appendix A), which is included in all boxes with the investigational device. It is stated in the IFU that the investigational device is for single-use only. Reprocessing, washing, disinfection, and sterilisation may compromise device characteristics, causing additional risk of physical harm to or infection of the user.

All PIs and designees will receive training by the sponsor in the handling and correct use of the investigational device. All training will be documented. For further details regarding the investigational device, please see the Investigators Brochure (IB)

4.6. Total number of devices intended for the clinical investigation

Approximately 20 randomized subjects will be included in this clinical investigation and have a TAI procedure performed at V1 and V2 with the investigational device or the comparator device in a randomized order. Following number of investigational devices, comparator devices and Peristeen Plus TAI systems intended for the clinical investigation will be needed:

560 investigational devices (140

these are driving for a high buffer when estimating the total number of the investigational devices needed for this clinical investigation.

- 28 Peristeen Plus rectal balloon catheters
- 64 Peristeen Plus TAI systems.

4.7. Description of the comparator device

In this clinical investigation the CE-marked Peristeen Plus rectal balloon catheter is used as a comparator device. The Peristeen Plus rectal balloon catheter will be used together with the CE-marked Peristeen Plus TAI system.

As the comparator device is already on the market and will be used within the intended use in this investigation, it is not considered as an investigational device according to ISO 14155:2020 and is thus not described in further details here.

Coloplast A/S will provide comparator devices to sites. To ensure that the site has enough supplies, more comparator devices than needed will be provided by Coloplast A/S.

4.8. Device accountability

All access to the investigational devices and comparator devices used in this clinical investigation is controlled by storage procedures and device accountability logs as described below. The investigational devices and comparator devices must only be used in this clinical investigation and only as stated in the clinical investigation plan (CIP).

Sponsor keeps a device accountability log that states the physical location of all investigational devices from shipment of investigations devices to the investigational sites until return of or disposal.

The PI or delegate keeps records documenting the receipt, use and return, and disposal of the investigational devices, which includes:

Name of device

- · Date of receipt
- Number of devices/retail boxes received
- · Identification of each investigational device (LOT number and item number)
- · The expiry date
- The date(s) of use
- Subject identification
- The date of return unused, expired or malfunctioning investigational devices.

5. Design of the clinical investigation

5.1. General

The clinical investigation is an exploratory, randomised controlled, open-labelled, crossover investigation (see figure 5). The clinical investigation will be conducted as a multi-centre clinical investigation in two different clinical investigation sites

The total clinical investigation duration for each subject will be up to 17 days, consisting of three site visits: Screening Visit (V0), Baseline Visit (V1) and Visit 2 (V2).

V0 and V1 can be performed on the same day. V1 and V2 must be scheduled on a day where the subject normally performs the TAI procedure, and V2 must furthermore be scheduled within 14 days after V1. At V1 and V2 the TAI procedure will be performed in a hospital setting.

Figure 5: Design of the clinical investigation

5.2. Primary endpoint

The primary endpoint is: Was it possible to perform transanal irrigation (assessed after irrigation at V1 and V2)? (Yes/no).

5.3. Assessments

5.3.4. Safety

- Adverse events
- Device deficiency.

5.4. Rationale for selection and measurement of endpoints

The endpoints and assessment have been selected to support the aim of the investigation exploring the feasibility of performing TAI with the investigational device.

The primary endpoint has been selected to evaluate if it is feasible to use investigational device for TAI to fulfil its intended purpose. Irrigation is defined according to the IFU and must be done with the regular volume of water used by the subject.

5.5. Demography and potential compromising factors

The following baseline data will be collected and reported at V1 by the PI or delegate:

Demographic information:

- Age at time of enrolment: Years
- Sex: Male, female
- Height: cm
- Weight: kg.

5.7. Randomisation Procedure

All subjects that have given informed consent and meet the inclusion and exclusion criteria will be randomised to one of two treatment sequences:

- First sequence: Investigational device at V1 and comparator device at V2
- Second sequence: Comparator device at V1 and investigational device V2.

The Rave RTSM[™] from Dassault Systèmes/Medidata is a validated computer randomization solution, that will be used for the randomization in this investigation. A randomization will be implemented, in which, subjects are to be randomly assigned to one of two sequences in block sizes of 4.

5.8. Blinding

Subjects and HCP will not be blinded in this investigation. Furthermore, since this is an exploratory investigation, Coloplast A/S personnel (e.g., CMs, Data Management Specialist, Biostatistican) will also not be blinded.

5.9. Total expected duration of the clinical investigation

The dates below are approximate, and no subjects will be enrolled before all required approvals have been obtained. If changes are required, applicable EC will be notified.

First patient in (FPI): April 2024

Last patient out (LPO): June 2024

Database lock (DBL): June 2024

Clinical Investigation Report (CIR): November 2024.

6. Clinical Investigation population

The clinical investigation will be conducted in approximately 20 randomized subjects enrolled in two clinical investigation sites

6.1. Eligibility criteria

To be included in the investigation, the subjects must comply with the selection criteria described below:

6.1.1. Inclusion criteria

For an eligible subject, all inclusion criteria described below must be answered "yes":

Table 1: Inclusion criteria

Inclusion criteria	Justification for inclusion criteria
1. Has given written informed consent	To meet the Helsinki declaration
2. Is at least 18 years old	To meet the Helsinki declaration
3. Has full legal capacity	To meet the Helsinki declaration
4. Has used TAI irrigation with balloon catheter for at least 4 weeks prior to inclusion	To ensure subjects can use TAI and is familiar with the sensation of a balloon catheter to be able to compare with the new rectal cathe- ter
5. Performs TAI minimum 3 times/week	To ensure a homogenous population that performs TAI on a regular basis for comparability within a relative small sample size
6. Is able to follow study procedures assessed by investigator	To ensure study completion of subjects

6.1.2. Exclusion criteria

For an eligible subject, all exclusion criteria described below must be answered "no":

Table 2: Exclusion criteria

Exclusion criteria	Justification for inclusion criteria
1. Has known anal or colorectal stenosis	IFU contraindication for TAI with Peristeen/Peristeen Plus
2. Has active/recurrent colorectal cancer	IFU contraindication for TAI with Peristeen/Peristeen Plus
3. Is within 3 month of anal or colorectal sur- gery	IFU contraindication for TAI with Peristeen/Peristeen Plus
4. Is within 4 weeks of endoscopic polypec- tomy	IFU contraindication for TAI with Peristeen/Peristeen Plus
5. Has ischaemic colitis	IFU contraindication for TAI with Peristeen/Peristeen Plus
6. Has acute inflammatory bowel disease	IFU contraindication for TAI with Peristeen/Peristeen Plus
7. Has acute diverticulitis	IFU contraindication for TAI with Peristeen/Peristeen Plus
8. Is participating in any other clinical study that may interfere with this study (assessed by investigator)	To ensure the scientific integrity of the study
9. Is pregnant or breastfeeding	IFU caution for TAI with Peristeen/Peristeen Plus

6.1.3. Pregnancy and breastfeeding

For female subjects with childbearing potential (they have had at least one period during the last 12 months), a urine pregnancy test will be performed at the Baseline Visit, to ensure the subject is not pregnant. The urine pregnancy test will be performed by dip-stick at the clinical investigational site. Furthermore, the female subjects should not be breastfeeding, when participating in the clinical investigation. If the subject becomes pregnant during the investigation, it is important, that the subject informs the PI or delegate representative immediately. The medical adviser will then consider whether she should continue in the investigation.

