7.2. Clinical investigation-related procedures

Visit 0 - Screening visit and study information:

- Introduction to the investigation and review of Subject Information Form/Informed Consent Form
- Scheduling V1 unless performed the same day as V0
- Register the potential subject on the pre-screening log.

Visit 1 - Inclusion and TAI procedure

- Introduction to the investigation reviewed and confirmed by subject
- Sign Informed Consent Form
- Allocation of subject ID number
- · For female subjects of childbearing potential urine pregnancy dipstick must be done
- Check of inclusion and exclusion criteria
- Obtain relevant medical history (assessed by PI)
- Collection of baseline data (see section 5.5)
- Randomization electronically in

Was it possible to perform the TAI procedure?

- Complete adverse events, device deficiencies, vigilance or protocol deviation forms, if applicable (see section 5.3.4)
- Complete Electronic Case Report Form (eCRF) incl. additional comments in comment field (if relevant)
- Schedule V2 (up to 14 days after V1)

Visit 2 - TAI procedure

Ensure the subjects well-being and that the subject is still comfortable to participate in the clinical investigation.

 Review for safety adverse events/serious adverse events/adverse device effects/protocol deviations/device deficiency

as it possible to perfe	orm the TAI proced	lure?		
omplete adverse ever	nts, device deficien	cies, vigilance form	or protocol deviation fo	rms, if applicable
	mplete adverse ever	mplete adverse events, device deficien	is it possible to perform the TAI procedure? mplete adverse events, device deficiencies, vigilance form mplete eCRF, including termination form and additional co	is it possible to perform the TAI procedure? mplete adverse events, device deficiencies, vigilance form or protocol deviation fo mplete eCRF, including termination form and additional comments in comment fie

Unscheduled visit/call

If an unscheduled visit/call is needed the unscheduled form in the eCRF must be completed.

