7.3. Flow-chart

Table 4: Connection between visits and assessments

Visit (V)	V0	V1	V2
Timing of visit (weeks)	0	0	1-14 days after V0
Activity			
Introduction to investigation and review of Subject Information Form/Informed Consent Form	х		
Signed Informed Consent		Х	
Allocation of subject number		Х	
Check of in- and exclusion criteria		Х	
Pregnancy test (urine dipstick) – for subjects of childbearing potential only		х	
Baseline information		Х	
Randomization		Х	
		Х	X
		Х	Х
		Х	Х
			Х
Assessment of subject's wellbeing and compliance with CIP		Х	X
AEs/ADEs/SAEs/SADEs/DD		Х	Х
Protocol deviations		Х	Х
Complete eCRF		Х	Х
Termination form			Х

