8.2. Risk-benefit for subjects participating in the clinical investigation

The clinical investigation is conducted in accordance with current law and applicable standards (see section 14). The rights, safety and well-being of human subjects shall prevail over the interest of science of society.

The study population will not include any vulnerable test subject such as children, pregnant or nursing women, or people with inability. MDR states a list of General Safety and Performance Requirements (GSPR) to be in compliance with. All GSPR are fulfilled for CP362 test catheter, except for those investigated in the clinical investigation. Relevant GSPRs for the clinical investigation can be found in Investigator's Brochure (Appendix 3). GSPR for CE-marked Peristeen Plus system are covered. Peristeen Gel is CE-marked under Medical Device Directive (MDD) under Peristeen Anal Plug certification and MDD extension (not under MDR), thus in compliance with MDD requirements.

To mitigate and reduce these risks, investigator/designees will be trained, according to the IFU, in correct handling of the investigator and comparator device. Furthermore, CP362 test catheters will be inserted by the study personnel and not the test subject. Test subjects will only use the test products for limited duration of time and under full supervision of the study personnel on site of the clinical investigation, and the test subjects will stay in hospital setting during the visit days. No test products will be handed out to the test subjects for independent use.

The transanal irrigation of subjects, with both investigational device and the comparator device will be performed by experienced HCP at investigational sites with many years of experience in conducting bowel management and with previous experience in working with clinical investigations.

The investigational setting is not expected to result in increased frequency or severity of the known risks associated with transanal irrigation. There are no direct benefits for the subjects involved; but, by participating in this investigation, the subjects will contribute with important information for developing improved solutions for bowel management that in turn may benefit individuals who are dependent on rectal catheters for bowel management. The subjects will be compensated for the time spent (see section 15).

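### The V1 pregnancy test depends only on a period in the last 12 months, so a woman of reproductive age without periods for another reason can enter with no required test

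*Combined protocol and SAP*

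**What the plan says.** Section 6.1.3 sets both the trigger and the purpose of the test. The trigger is menstrual history: "For female subjects with childbearing potential (they have had at least one period during the last 12 months), a urine pregnancy test will be performed". The timing and purpose follow directly: "at the Baseline Visit, to ensure the subject is not pregnant". The same section adds that "the female subjects should not be breastfeeding, when participating in the clinical investigation".

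Section 7.2 makes the test a Visit 1 procedure: "For female subjects of childbearing potential urine pregnancy dipstick must be done". Table 4 in section 7.3 schedules it at V1 "for subjects of childbearing potential only". Neither place redefines childbearing potential, so both depend on the bracket in 6.1.3.

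The restriction on entry is wider than the trigger. Exclusion criterion 9 in section 6.1.2 reads "Is pregnant or breastfeeding", with no reference to menstrual history. Section 8.2 states: "The study population will not include any vulnerable test subject such as children, pregnant or nursing women, or people with inability".

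**The concern.** The exclusion covers all women, while the only prescribed check covers a subset chosen by bleeding history. A year without periods shows that a woman cannot conceive only if its cause is loss of fertility. Where the cause is something else, such as hormonal contraception or illness, the rule as written puts a woman who may still be able to conceive in the untested group. A missed period cannot alert such a woman or her investigator to a pregnancy, so her history is less informative here than for other women.

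What is at stake is eligibility and, to a small degree, subject safety. Section 2 describes this as a first-in-human investigation, and section 8.2 gives an unqualified assurance that pregnant women will not be included.

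**Working it through.** The plan states no figure on this point, so there is nothing to reproduce. The check compares the sections, adds one date calculation, and ends with a labelled illustration of size.

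**1. Who is barred, who is tested, who can enter**

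| Question | Source | Answer |
|---|---|---|
| Who is barred for pregnancy? | 6.1.2 criterion 9; 8.2 | Every pregnant woman |
| Who must be tested? | 6.1.3; 7.2; Table 4 | Only women with a period in the preceding 12 months |
| Does age or menopausal status limit entry? | 6.1.1, Table 1 | Minimum age 18; no upper limit, no menopausal criterion |
| Is another pregnancy check named for the rest? | 6.1.3; 7.2; 7.3 | None in the available text |

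The first two rows cover different groups, and the third shows that women in the difference can enrol. Some procedure lines in 7.2 and rows in Table 4 are redacted, but the pregnancy-test entries in 6.1.3, 7.2 and Table 4 are legible.

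**2. Which pregnant women the trigger would miss**

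Assumption, not in the documents: pregnancy lasts up to about 280 days from the last period, or about 266 days from conception.

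- Woman with regular periods, pregnant at V1: her last period was at most about 280 days earlier. 280 < 365, so she meets the definition and is tested.
- Pregnant woman who is missed: her last period was more than 365 days before V1. If conception was *x* days before V1, with *x* between 0 and 266, she had gone more than 365 − *x* days without a period when she conceived. At *x* = 266 this is 365 − 266 = 99 days; at *x* = 0 it is 365 days.

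The gap is therefore confined to women with a long absence of periods, from roughly 99 up to 365 days before conception, who can still conceive.

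**3. Size**

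The documents give no expected sex or age mix and no data on contraception. Purely as an illustration, suppose 6 to 10 of the 20 subjects were women of reproductive age and 10% to 25% of them had no periods for such reasons. The number entering without a required test would be:

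- low end: 6 × 0.10 = 0.6
- high end: 10 × 0.25 = 2.5

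These would be untested women, not pregnancies; the expected number of pregnancies would be far smaller. All four inputs are assumptions, and the gap in the rule does not depend on them.

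**The case against.** A reader might infer more than the documents support, and the other side is right on several points.

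- **That the test cannot serve its stated purpose.** It can, for the women 6.1.3 defines. By the date check, these include women with regular periods who are pregnant at V1.
- **That exclusion 9 is not enforced.** It applies to every subject. Section 7.2 requires a check of the criteria at V1 and lists relevant medical history, assessed by the principal investigator, before randomisation. No test is prescribed for stenosis, cancer or colitis either, and nothing forbids testing more women.
- **That breastfeeding women without periods slip through.** They are excluded separately by criterion 9 and by 6.1.3.
- **That the safety exposure is large.** Table 2 justifies criterion 9 by an IFU caution, whereas criteria 1 to 7 rest on contraindications. If pregnancy occurs during the study, 6.1.3 leaves continuation to the medical adviser's consideration. Subjects already irrigate at least three times a week, and the test catheter is assigned at one of two visits, inserted by study personnel under supervision in hospital.

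All of this limits the weight of the point, but none of it supplies a check for women outside the definition. The plan does not rely on history for the other women, since it makes a dipstick mandatory for them. For the remainder it relies on history without saying so, and with Table 4 worded as a restriction, the two sites could reasonably act differently.

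**Conclusion.** The point holds as an incomplete trigger for a safety check, and it is minor. Followed as written, section 6.1.3 classes a woman of reproductive age with no period for 12 months as not of childbearing potential, whatever the cause. She then enters without a required test, and criterion 9 rests on history alone.

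The number affected cannot be determined from the documents and is probably very small among about 20 subjects. The conclusion rests on one premise from general knowledge: that some women without periods for a year can still conceive. The primary endpoint, the Fisher's exact comparison, the 5% level and the sample size are unaffected.

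**What to change.** Reconcile section 6.1.2 (criterion 9), section 6.1.3, section 7.2, Table 4 in section 7.3 and section 8.2 so that two things are clear:

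1. Absence of a period for 12 months does not by itself exempt a woman from the dipstick already scheduled at V1.
2. Criterion 9 is checked in every woman who could be pregnant, and the plan says how.

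The exact definition of childbearing potential is a clinical matter for the sponsor and its medical adviser; none is proposed here. Whatever is chosen should be stated once in 6.1.3 and referred to in 7.2 and Table 4.

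The cost is a short text change through the amendment procedure in section 12 and a few additional dipsticks at V1. No visit, endpoint or analysis changes.
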